8.2.4 Durable Response Rate

A response with a duration > 6 months is considered a durable response, and the DRR is defined as the proportion of subjects in the Full Analysis Set with a durable response.

Summary will also be provided for clinical benefit rate which is defined as the proportion of subjects who have achieved a CR, PR or SD assessed at least 28 days after the first dose date of tabelecleucel.

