## **VII. Criteria for Diagnosing and Grading Endpoints of Interest**

- 1) Acute toxicities induced by infusions of EBV-specific T-cells will be graded according to the NCI criteria used to grade organ toxicities induced by chemotherapeutic agents (48).
- 2) Allograft rejection episodes developing in organ transplant recipients will be diagnosed, assessed, and managed by the patient's transplant physician, utilizing standard criteria established for the identification and grading of rejection episodes in transplanted kidney, liver, heart or lung allografts (49-51).
- 3) Acute Graft vs. Host Disease will be diagnosed and graded utilizing the IBMTR consensus criteria (47) and the histopathological criteria of Slavin and Woodruff (52). Chronic graft vs. host disease will be diagnosed and graded using the staging criteria developed by Sullivan et al (53).
- 4) The responses of the EBV lymphomas will be identified as complete remission, partial remission, stable disease, or no response with disease progression based on the following criteria:

- Complete remission: Complete resolution of all clinical and radiologic evidence of lymphoma, confirmed by biopsy of affected tissues when indicated, lasting for at least three weeks following completion of a course of cell infusions.
- Partial remission: A 50% or greater reduction in the size of all lymphomatous lesions as determined by CT or MRI based measurements of tumor volume, which is maintained for at least three weeks following completion of a course of cell infusions.
- Stable disease: Less than 50% reduction of lymphomatous lesions without progression at any site maintained for at least 3 weeks following completion of a course of cell infusions.
- No response with disease progression: Progressive enlargement of one or more lymphomatous lesions by three weeks following a course of T-cell infusions.

5) For recipients of HSCTs, and other severely immunocompromised patients who have high and increasing levels of EBV DNA in the blood, without clinical or radiological evidence of tumors, who are treated preemptively with EBV-Specific T cells, a therapeutic response will be defined as:

- Viral - Complete Response: Clearance of EBV without subsequent development of EBV LPD
- Viral - Partial Response: At least a ten-fold decrease in EBV DNA levels
- Viral - Stable Response: Persistence of circulating EBV DNA without development of EBV LPD

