6 GENERAL PRINCIPLES

6.1 General

The Full Analysis Set will be used for all the safety analyses and efficacy analyses except endpoints of DOR and TTR, which will be conducted on the subjects in the full analysis set with an objective response (CR or PR). Some analyses may be repeated in the selected subgroups specified in Section 4.3 depending on data availability.

Unless otherwise specified, all continuous variables will be summarized using descriptive statistics, which will include the number of subjects with a valid measurement (n), mean, standard deviation (SD), median, 25% quantile (Q1), 75% quantile (Q3), minimum and maximum. All categorical variables will be summarized using frequencies and percentages. The exact binomial 2-sided 95% confidence interval (CI) will be provided for all binary efficacy endpoints, including ORR and DRR. Kaplan-Meier (K-M) estimates along with their corresponding 95% CI will be calculated for time-to-event endpoints.

The following terms may be used for this SAP and tables, figures and listings (TFLs):

- **Study treatment:** Study treatment refers to all the protocol specified treatment administered to subjects.
- **Enrolled subjects:** refers to subjects who receive study treatment.
- **Enrollment date:** refers to the date that the informed consent form was signed.
- **Study day:** The subject's time on study will be determined in study days. Day 1 is defined as the day of the first study treatment administration. Study day is defined as the date of interest minus day 1 plus 1 if the date is on or after day 1. If the date is before day 1, the study day is defined as the date of interest minus day 1.
- **Baseline:** refers to day 1 prior to the first administration of study treatment. The baseline value of a parameter (eg, laboratory tests and efficacy endpoints) is defined as the last value prior to the first study treatment administration.
- **Duration of treatment:** defined as the date of the last dose of study treatment minus the date of the first dose of study treatment + 1
- **Treatment exposure period:** from day 1 through 30 days after the last administration of study treatment.
- **Restriction Switch:** Subjects could change to tabelecleucel with a different HLA restriction from a different donor either due to a lack of efficacy from the current cell line or insufficient supply. "Restriction switch" refers to only the change to tabelecleucel with a different HLA restriction due to lack of efficacy.

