8 EFFICACY ANALYSES

For the primary efficacy analysis, all response assessment data will be included regardless of how many Restriction Switches the subjects had.

Efficacy analyses will be conducted by cohorts and combined cohorts, as specified in Section 4.2.

Disease assessments performed by investigators regardless of modalities will be grouped into one timepoint assessment if the gap between two consecutive disease assessments is less than or equal to 14 days. This grouping will continue for the same timepoint assessment until the gap between two consecutive disease assessments exceeds 14 days.

The ranking for assessment modalities is specified in Table 2. If there are multiple assessments with the same modality in the same timepoint assessment, the worst/worse assessment (from the best to the worst in the order of not evaluable [NE], CR, PR, stable disease [SD] and progressive disease [PD]) will be selected for that modality. If there are assessments based on multiple modalities for a timepoint assessment, then the overall response for the timepoint assessment will be decided by the rank of the modalities specified in Table 2. For example, for a timepoint assessment, a PR was assessed per biopsy and a CR was assessed per physical examination. The assessment per biopsy will override that of physical examination for this timepoint assessment. If PD is determined as the response for a timepoint assessment, the earliest assessment date among all the disease assessments for this timepoint assessment will be considered as the PD date. If SD, PR or CR is determined as the response for a time assessment, the latest assessment date among all the disease assessments for this timepoint assessment will be considered as the response date.

While in general if any therapy directed towards the disease being treated, other than protocol-specified treatment, is initiated, response data after the initiation date of such therapy may be censored. However, given the fact that some anti-underlying disease therapies were actually allowed per the protocol, in the primary analysis of disease assessment related endpoints, none of such therapies were considered for censoring rule. As a sensitivity analysis, response data after the initiation of such therapies are censored, and such analysis is conducted for the endpoints including ORR, DOR, and PFS based on the Full Analysis Set.

Table 2: Rank of the Modalities (1 indicates highest rank)

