8.2.3 Progression-free Survival

Progression-free survival is defined as the time from the first dose of study treatment to either of following events whichever occurs first: (1) progression after the last response or (2) death due to any cause.

Death within 90 days after last valid disease evaluation (ie, not NE), or first study treatment dose date if there is no valid post-baseline disease evaluation, will be counted as events in the PFS definition

For subjects without an event as defined above, PFS will be censored at

- Last valid (not NE) post -baseline disease evaluation date
- First dose date if there is no valid post-baseline disease evaluation.

As a sensitivity analysis, PFS will be defined as the time from the first dose of tabelecleucel to either of following events, whichever occurs first, (1) the first progression or (2) death due to any cause. All other details and censoring rules are the same as above for the primary PFS analysis.

In another sensitivity analysis, if any anti-underlying disease therapy is initialized before the event date/censoring date, PFS is censored at the last assessment date prior to the therapy initialization.

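### The clinical benefit rate has a 28-day floor but no condition on earlier progression, so stable disease recorded after progression counts as benefit

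*SAP*

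**What the plan says.** SAP section 8.2.4, after defining durable response, adds a summary of clinical benefit: "the proportion of subjects who have achieved a CR, PR or SD assessed at least 28 days after the first dose date of tabelecleucel". The only time condition is the 28-day minimum. There is no upper limit and no reference to what earlier timepoints showed.

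The other relevant rules are these.

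- **Data kept.** For the primary efficacy analysis, SAP section 8 says that "all response assessment data will be included regardless of how many Restriction Switches the subjects had". Under SAP section 6.1 a Restriction Switch "refers to only the change to tabelecleucel with a different HLA restriction due to lack of efficacy".
- **Other therapy.** SAP section 8 says that "in the primary analysis of disease assessment related endpoints, none of such therapies were considered for censoring rule". A censored version is planned as a sensitivity analysis: "such analysis is conducted for the endpoints including ORR, DOR, and PFS based on the Full Analysis Set".
- **Conflicting assessments.** SAP section 8 takes the worst result only in a limited setting: "If there are multiple assessments with the same modality in the same timepoint assessment, the worst/worse assessment" is selected for that modality.
- **Progression in PFS.** The primary event in SAP section 8.2.3 is "1) progression after the last response or (2) death due to any cause". A first-progression version is a sensitivity analysis.
- **Stable disease.** The protocol's endpoint criteria (item 4) define it as "Less than 50% reduction of lymphomatous lesions without progression at any site maintained for at least 3 weeks following completion of a course" of infusions.

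**The concern.** A clinical benefit rate is normally read as the share of patients whose disease was controlled. Under the SAP's wording, one SD timepoint on or after day 28 is enough, whatever came before it. A patient who progressed and later had a scan called stable counts the same as a patient who never progressed.

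The trial gives this sequence room to arise. Patients may change cell line because the first one failed, and the protocol's post-infusion section allows alternative treatment after progression. Assessments after either event stay in the primary analysis. SD that follows failure of the T-cells and the start of something else could then be credited to the T-cells.

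One qualifying timepoint settles a subject's status for good. Further timepoints can therefore only leave the rate level or raise it, and patients followed longer have more chances to qualify. The trial has no control arm and SAP section 11 plans no formal test on CR, so readers will take the descriptive rates at face value.

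**Working it through.** The documents give no target, expected value or sample size for this rate, so there is no planned figure to reproduce. The check applies the definition to short response records and then looks for a rule elsewhere that would change the result.

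**1. Assessment days.** Infusions fall on days 0, 7 and 14 (+/- 3 days) (protocol, Treatment Plan VI), with imaging three weeks after each course (Treatment Plan VIII).

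- First scan: 14 + 21 = day 35. If the third infusion moves by 3 days: 11 + 21 = 32 to 17 + 21 = 38.
- Second scan, if course 2 starts on day 35: 35 + 14 + 21 = day 70.

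The 28-day floor is already met at the first on-schedule scan, so it does not screen out earlier progression.

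**2. Classification.** The records are hypothetical. Timepoints in each are more than 14 days apart (35 - 20 = 15; 70 - 35 = 35), so the SAP's grouping rule does not merge them.

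| Record | As written | SD counted only if no earlier PD |
|---|---|---|
| PD day 35, SD day 70 | benefit | no benefit |
| PD day 20, SD day 35 | benefit | no benefit |
| SD day 35, PD day 70 | benefit | benefit |
| PD day 35, PD day 70 | no benefit | no benefit |
| SD day 20, PD day 35 | no benefit | no benefit |

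Only the two PD-then-SD records change.

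**3. Does another rule close the gap?**

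- The worst-assessment rule works within one timepoint and one modality. It does not carry PD forward to a later timepoint.
- The SAP has no best-overall-response rule that stops at first PD.
- The protocol's SD definition looks at the three weeks after a course. SD after a later course can meet it despite PD after an earlier one.
- The first-progression rule applies only to a PFS sensitivity analysis.
- The censored sensitivity analysis names ORR, DOR and PFS. Its list is introduced as non-exhaustive, but clinical benefit is not on it.

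**4. Size, by assumption.** If k of n subjects qualify only through SD after PD, the rate rises by k/n. Take n = 20 with 12 subjects benefiting without earlier PD (both figures assumed), with exact binomial 95% intervals as in SAP section 6.1:

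| k | Rate as written | 95% CI |
|---|---|---|
| 0 | 12/20 = 60% | 36% to 81% |
| 1 | 13/20 = 65% | 41% to 85% |
| 2 | 14/20 = 70% | 46% to 88% |
| 4 | 16/20 = 80% | 56% to 94% |

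**The case against.** The strongest reply is that this is a choice of estimand on a minor quantity. Clinical benefit is neither the primary endpoint (SAP 3.1) nor one of the six secondary endpoints (SAP 3.2), and no decision depends on it. The SAP also means to credit disease control after early failure: it keeps data across Restriction Switches, and DOR, PFS and TTP all look to progression after the last response. The protocol further limits the sequence. Repeat Group I courses and additional Group II courses require no significant progression, although the second Group II course carries no such condition. Patients who progress may leave for other treatment and then be assessed only as clinically indicated.

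The low stakes and the limits on frequency stand. The estimand argument stands for CR and PR but not for SD. The last-response approach is built around responses; SD is not a response, and nothing in the SAP extends the approach to it.

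Three stronger readings are tempting, and the documents do not support them.

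- **That the SAP contradicts the protocol's definition of SD.** The protocol's no-progression condition is tied to a course of infusions, so it does not bar SD after progression on an earlier course.
- **That 28 days is too short because three weeks after the third infusion is day 35.** The floor filters SD calls already made by the investigator and does not redefine SD. A 35-day minimum would reject on-schedule scans on days 32 to 34.
- **That SD after progression is easy to reach because growth is judged against a new, larger reference, so the rate merely records survival to another scan.** Neither document says the reference resets, and the later scan must still be judged stable.

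**Conclusion.** The gap is real on the text. The clinical benefit rate has no condition on earlier progression and no other rule supplies one, so a non-responder with PD and then SD counts as benefiting. Among non-responders the effect runs one way, upward, by k/n.

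The size of k is unknown. The 5, 10 and 20 point increases above (1/20, 2/20, 4/20) rest on an assumed cohort and an assumed number of such subjects. A reader might infer that the reported rate is in fact inflated; the documents show only that the definition permits it. No planned test, sample size or listed endpoint is affected, so this is a matter of making a descriptive rate mean what its name suggests.

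**What to change.** Add one clause to the clinical benefit sentence in SAP section 8.2.4: SD counts only if no PD timepoint precedes it. Keep the 28-day floor, and say whether it governs CR and PR as well as SD. CR and PR may still count after PD, in line with the SAP's approach to DOR, PFS and TTP.

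Report the as-written rate next to the restricted one, so that SD after a Restriction Switch stays visible. This mirrors the SAP's existing pairing of last-response and first-progression PFS.

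The cost is one sentence, a small programming change and an extra row in the table. No new data are needed. The main rate may be somewhat lower.

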8.2.5 Time to Progression

Time to progression (TTP) is defined as the time from the date of the first dose of study treatment to progression after the last response. Death within 90 days after the last valid post-baseline disease evaluation, or after first dose date if there is no valid post-baseline disease evaluation, will be counted as an event only if the death reason is due to disease progression. Data will be censored on the death date if such deaths are not due to disease progression. The other censoring rules are the same as the ones used for the primary analysis of PFS in Section 8.2.3.

8.2.6 Time to Response

Time to response (TTR) is calculated only for subjects who achieve CR or PR on study. TTR is defined as the time from the date of the first dose of tabelecleucel to the date of the response (PR or CR whichever occurs first). Descriptive statistics will be provided. Similarly, time to best response will also be summarized for subjects who achieve CR or PR.

8.3 Subgroup Analysis

The analysis of ORR and OS will be repeated for the subgroups defined in Section 4.3.

9 PHARMACOKINETIC/PHARMACODYNAMIC ANALYSIS

No pharmacokinetic/pharmacodynamic analysis is planned.

10 SAFETY ANALYSIS

For subjects who were assigned to 2 cohorts, safety summaries for the first cohort will include data up to the day prior to the first dose date of study treatment in the next cohort. For summaries

of laboratory parameters, the baseline data for the second cohort will be the last laboratory parameter prior to the date of the first dose of study treatment in the next cohort.

10.1 Summary of Serious Adverse Events

Only serious adverse events (SAEs) were systematically collected in this study, hence all adverse event (AE) summaries will be based on SAEs only. Non-serious AEs will be listed if any.

The Medical Dictionary for Regulatory Activities version 22.0 will be used to code the SAEs to a system organ class (SOC) and a preferred term (PT) within the SOC. The Common Toxicity Criteria for Adverse Events (CTCAE) version 4.0 was used to grade the severity of SAEs.

Treatment-emergent serious adverse events (TESAEs) are defined as follows:

- any SAE that occurred after initiation of the first dose of study treatment through 30 days after the last dose of study treatment or
- any SAE that occurred prior to the first dose but worsened after the first dose or
- any related SAE with a date of onset on or after the first dose of study treatment.

SAEs occurring on the same day as the first dose of study treatment will be counted as treatment-emergent.

All the SAEs collected in this study will be listed.

All TESAEs will be summarized as follows.

- Overall summary of subject incidence for the following TESAE categories (repeat for the subgroups listed in Section 4.3)
 - Any TESAEs
 - TESAEs with worst grade ≥ 3
 - Fatal TESAEs
 - Any Treatment related TESAEs
 - Treatment related TESAEs with worst grade ≥ 3
 - Treatment related Fatal TESAEs
- Subject incidence for the following categories of TESAEs will be summarized by PT in descending order of frequency
 - TESAEs (repeat for the subgroups listed in Section 4.3)
 - Treatment-related TESAEs (repeated for < 16 vs. ≥ 16 and < 18 vs. ≥ 18 years age subgroups)
 - Fatal TESAEs (repeated for < 16 vs. ≥ 16 and < 18 vs. ≥ 18 years age subgroups)
 - Fatal TESAEs

- Subject incidence for the following categories of TESAEs will be summarized in descending order of frequency by PT and worst grade
 - TESAEs
 - TESAEs with worst grade ≥ 3 (repeat for the subgroups listed in Section 4.3)
 - Treatment-related TESAEs
- Subject incidence of the following categories of TESAEs will be tabulated SOC and PT in descending order of frequency by SOC and then PT within an SOC:
 - TESAEs
 - Treatment-related TESAEs

10.2 Summary of Laboratory Results

Routine clinical laboratory data (ie, hematology and serum chemistry) will be processed by local laboratories. Atara Biotherapeutics will convert the original test results/units to standard and conventional results/units and grade lab test results based on the CTCAE version 4.03 grading and corresponding normal ranges from University of California San Francisco (UCSF)¹ for the lab parameters.

In case the lab test result is less than the lower limit of quantification (LLOQ), a value of half the LLOQ will be used as the numerical test result. If the lab test result is greater than the upper limit of quantification (ULOQ), the ULOQ will be used as the numerical test result.

10.2.1 General Presentation of Laboratory Data

Summary of selected laboratory tests (Appendix 13.1 Selected Laboratory Tests) will include only data collected up to the last dose of study treatment plus 30 days.

For selected laboratory parameters, descriptive statistics of actual values and changes from baseline for the post-baseline laboratory data will be summarized for each visit window. Descriptive statistics of the minimum and maximum post baseline values for each subject will also be summarized. In the case of multiple values in an analysis window, data will be selected for analysis as described in Section 6.3. If either the baseline or post-baseline value is missing, the observation will not be included in the change from baseline summary.

The percentage of change from baseline (mean \pm SD) for selected lab parameters vs. visit window, will be plotted.

In addition, grade shift tables from baseline to worst on-treatment value will be provided for selected laboratory parameters.

For laboratory tests with criteria for both increased and decreased levels, analyses for each direction (ie, increased, decreased) will be presented separately.

¹ Available at: <http://labmed.ucsf.edu/sfghlab/test/ReferenceRanges.html>

In addition, data for sirolimus, tacrolimus and interleukin 6, highly sensitive will be provided in listings.

10.2.2 Treatment-Emergent Laboratory Abnormalities

Treatment-emergent laboratory abnormalities are defined as values that increase by at least 1 toxicity grade from baseline at any post baseline time point, up to and including the date of last dose of tabelecleucel plus 30 days. If the relevant baseline laboratory value is missing, any abnormality of at least grade 1 observed at any post baseline time point up to and including the date of last dose of tabelecleucel plus 30 days will be considered treatment emergent.

Number of subjects (%) with treatment emergent laboratory abnormalities will be summarized for selected laboratory parameters (Appendix 13.1 Summery of Selected Laboratory Tests). The number of subjects with any post baseline value for each laboratory test will be the denominator for the percentage of subjects with the corresponding treatment-emergent laboratory abnormality.

